Official Title: Determination of Metabolomic Profile Differences in Sarcopenia Accompanying Fibromyalgia Syndrome

NCT Number: Not yet assigned (Initial Submission)

Document Date: Jan 25, 2023

STUDY PROTOCOL AND STATISTICAL ANALYSIS PLAN

This study was conducted in a single-center, cross-sectional observational design. The study complied with the Declaration of Helsinki and was approved by the Ankara Bilkent City Hospital No. 2 Clinical Research Ethics Committee with the number E2-22-1740. Informed consent was obtained from all individual participants included in the study. This study included 44 female patients aged 18-60 who were diagnosed with fibromyalgia according to the ACR (American College of Rheumatology) 2016 diagnostic criteria and applied to Ankara Bilkent City Hospital Physical Therapy and Rehabilitation Hospital outpatient clinics between May 2022 and December 2022 and 22 female healthy controls. Female volunteers who applied to Ankara Bilkent City Hospital Physical Therapy and Rehabilitation Hospital outpatient clinics for other reasons and who did not have any accompanying diseases such as fibromyalgia and sarcopenia constituted the healthy controls. Exclusion criteria include cognitive dysfunction; history of serious cardiac disease, COPD (Chronic Obstructive Pulmonary Disease), epilepsy, malignancy, neuromuscular disease, inflammatory rheumatic disease, endocrine disease and organ failure; currently pregnant; use of systemic glucocorticoid, ACE inhibitor, angiotensin receptor blocker, statin, sulfonylurea; male gender. Fibromyalgia is more common in women. Gender differences may affect metabolome results. That's why all participants in the study were women.

Demographic data, medication use and disease duration of the participants were recorded. Patients with fibromyalgia and healthy volunteers were screened for sarcopenia by using hand grip strength measurement with a hand dynamometer, muscle mass measurement

with bioimpedance analysis. According to EWGSOP2 (European Working Group on Sarcopenia in Older People) criteria, patients with hand grip strength below 16 kg were considered to have probable sarcopenia. 22 participants were included in the FMS PS- (Fibromyalgia Syndrome without Probable Sarcopenia) group and 22 participants were included in FMS PS+ (Fibromyalgia Syndrome with Probable Sarcopenia) group. The hand grip strength of all individuals in the healthy control group was over 16 kg.

Plasma samples were collected from all participants. Samples were centrifuged at 1500 rpm for 10 minutes and stored at -80 degrees to be used in metabolome analysis.

Measurement of plasma metabolomics

A mixture of methanol/water (90%:10% v/v) was added onto 100 μ L of plasma. The samples were kept at -20°C overnight. The obtained samples were centrifuged at 15000 rpm for 10 minutes. Proteins precipitated and metabolites remained in the methanol/water mixture. The resulting metabolite mixture was placed in a vacuum centrifuge to remove methanol and water. 20 μ L methoxyamine (20mg/20 μ L) was added to the resulting metabolites. Afterwards, the samples obtained after derivatization with 80 μ L MSTFA + 1% TMCS were analyzed by gas chromatography/mass spectroscopy (GC/MS).

Schimadzu qp2010 device was used in the analyses. In this study, FAME mix standards were used as standards in the system. DB-5MS stationary phase column (30 m+10m DuraGuard x 0.25mm i.d. and 0.25- μ m) was used in the analysis. The oven temperature was fixed at 70°C for one minute, then increased to 320°C in increments of 10 degrees per minute and remained for 10 minutes. Afterwards, the system returned to its original temperature. The analysis took a total of 37 minutes. In the GC/MS system, the scanning range was 50-600 m/z.

The obtained GC/MS data were evaluated on the MS-DIAL metabolomics platform. Untargeted metabolomics studies have been conducted. Metabolites with a match score of 70

and above were accepted using the Kovats retention index database. In the pre-data analysis processes within the MS DIAL platform, peak identification, deconvolution and data alignment processes were primarily carried out. Subsequently, the structures of the metabolites were elucidated. Peak areas and heights were used in semi-quantitative analysis. Normalization processes were also carried out according to the total ion chromatogram. Two-tailed t-test was performed between experimental groups and significantly changed metabolites were identified. Metaboanalyst 4.0 platform and KEGG (Kyoto Encyclopedia of Genes and Genomes) database were used in pathway analyses.

Statistical Analysis

SPSS (Statistical Package for Social Sciences) 22.0 Statistical Package Program and MS-DIAL metabolomics platform were used to evaluate the data. After determining whether the data showed normal distribution, statistical evaluation was made with appropriate parametric or non-parametric tests. The numerical data obtained are given as mean and standard deviation, and categorical data are given as number (n) and percentage (%). Descriptive statistical methods (Mean, Standard deviation, upper and lower values) were used when evaluating the data. After comparing the metabolome data between the three groups, cluster analysis was performed and pathway differences between the groups were revealed. The results were evaluated at the 95% confidence interval and the significance level was $p<0.05$.

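### The only within-fibromyalgia contrast (PS+ vs PS-) is unadjusted, and the recorded disease duration has no described role in it, so a duration difference could be reported as a probable-sarcopenia profile

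*Combined protocol and SAP*

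**What the plan says.** The combined protocol and SAP is a short document, and its opening section is unnumbered. That section gives the design: "This study was conducted in a single-center, cross-sectional observational design". It describes three groups of women.

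- Fibromyalgia: "This study included 44 female patients aged 18-60 who were diagnosed with fibromyalgia". They are split 22 and 22 by grip: "patients with hand grip strength below 16 kg were considered to have probable sarcopenia".
- Controls: 22 women "who did not have any accompanying diseases such as fibromyalgia and sarcopenia constituted the healthy controls". In addition, "The hand grip strength of all individuals in the healthy control group was over 16 kg".

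Muscle mass was measured by bioimpedance, but the stated rule for group membership uses grip only.

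On covariates, the same section says "Demographic data, medication use and disease duration of the participants were recorded". Disease duration is not named again.

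Under Measurement of plasma metabolomics, the group comparison is: "Two-tailed t-test was performed between experimental groups and significantly changed metabolites were identified". Under Statistical Analysis, the plan adds a choice of parametric or non-parametric tests after a normality check, descriptive statistics, a three-group comparison of the metabolome followed by cluster and pathway analysis, and a 5% significance level. No covariate model, matching, stratification or sensitivity analysis is described.

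**The concern.** The title asks about sarcopenia accompanying fibromyalgia. PS- vs control contrasts fibromyalgia and not sarcopenia, and PS+ vs control mixes the two conditions. PS+ vs PS- therefore has to carry the question.

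Nothing in the design balances those two groups on the course of the disease. Grip strength was observed, not allocated, and there is no low-grip group without fibromyalgia to help separate the explanations. If PS+ and PS- differ in how long they have had fibromyalgia, any metabolite related to duration will differ between them even if it has nothing to do with muscle. An unadjusted t-test cannot tell these cases apart, and what it flags is carried forward to pathway interpretation. The variable that would test this explanation has been collected, but the plan does not say that it enters the comparison.

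**Working it through.** **No figure to reproduce.** The plan states no effect size, SD, power or sample-size calculation. Its counts agree: 22 + 22 = 44 patients.

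**Inputs from the plan.** n = 22 per group; two-tailed two-sample t-test; significance level 0.05; no covariate.

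**Assumed inputs (the plan gives neither).**
- D: PS+ minus PS- difference in disease duration, in within-group SDs. Range 0.5 to 1.0, with 0 as reference.
- r: within-group correlation between duration and a metabolite. Range 0.2 to 0.5.
- The metabolite has no true relation to probable sarcopenia.

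**Step 1, spurious shift.** With unit within-group SD, the expected group difference is D × r. Example: 0.5 × 0.2 = 0.10 SD; 1.0 × 0.5 = 0.50 SD.

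**Step 2, noncentrality.** D × r × √(22/2) = D × r × 3.317. Example: 0.10 × 3.317 = 0.332; 0.50 × 3.317 = 1.658.

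**Step 3, chance of p < 0.05.** Degrees of freedom are 22 + 22 − 2 = 42, with two-sided critical value 2.018. The noncentral t distribution gives:

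| D | r = 0.2 | r = 0.3 | r = 0.4 | r = 0.5 |
|---|---|---|---|---|
| 0 | 5.0% | 5.0% | 5.0% | 5.0% |
| 0.5 | 6.2% | 7.7% | 9.9% | 12.8% |
| 0.8 | 8.1% | 12.2% | 17.9% | 25.4% |
| 1.0 | 9.9% | 16.3% | 25.4% | 36.7% |

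These are rates per metabolite. The result depends on both assumptions: at r = 0.2 the inflation is modest throughout, and without imbalance there is none.

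**Step 4, does adjustment repair it?** Fitting group plus duration to simulated data (40,000 runs per cell; D = 0.5, 0.8, 1.0; r = 0.2, 0.3, 0.5) gave false-positive rates of 4.8% to 5.3%.

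**Step 5, price in precision.** The unadjusted standard error of the difference is √(2/22) = 0.30 SD. The adjusted one is approximately √(1 − r²) × √(2/22 + D²/42).
- D = 0.5, r = 0.5: 0.866 × 0.311 = 0.27 SD.
- D = 1.0, r = 0.2: 0.980 × 0.339 = 0.33 SD.

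So adjustment can narrow the interval slightly or widen it by about a tenth (0.33/0.30). Residual degrees of freedom fall from 42 to 41.

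**The case against.** The strongest reply has four parts.

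*Duration may already be covered.* The Statistical Analysis section gives numerical data as mean and SD with suitable tests, and duration is numerical. A reader might infer from the plan's silence that duration is never used at all. The text does not support that, because a by-group table, and even a test of duration between groups, would fall within it. What stands is narrower: no described step uses duration to match, stratify or adjust the metabolite comparison, and a table does not adjust anything.

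*The mechanism is not documented.* The plan does not say that grip falls with longer fibromyalgia, or that any metabolite tracks duration. This is right. A reader might infer that PS+ women do have longer disease and that the objective therefore goes unanswered, but no group values are given. Only the possibility is established.

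*Severity is not in the documents.* It is tempting to say that the PS+ profile is really a profile of worse fibromyalgia, and to adjust for symptom scores. The plan only names the diagnostic criteria and lists no pain, symptom or severity score as recorded, so neither step has a basis in the text. Nor is duration shown to stand in for severity. This objection stands in full and limits the point to duration.

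*Duration is one covariate among several.* Age and medication use are recorded in the same way, also without a described role in the comparison, and duration may track age. A duration-adjusted result therefore cannot be credited to disease course alone. This is fair, but it does not remove the gap for duration.

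**Conclusion.** The point holds, limited to recorded disease duration. The plan's one within-fibromyalgia contrast is non-randomised, defined by grip alone and unadjusted, and a relevant variable already in hand has no described part in it.

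The size is conditional. It is about 6% to 37% per metabolite instead of 5% over the assumed ranges of D and r, and exactly nominal if duration is balanced. These figures also assume approximately normal data and a linear relation between metabolite and duration. The documents do not show that bias occurred, and they do not support the claim that the findings reflect fibromyalgia severity. This is a worthwhile improvement to the analysis; it does not show that the study fails.

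**What to change.** 1. Report disease duration by group for PS+ and PS-.
2. For PS+ vs PS- (n = 44), fit each metabolite on group plus disease duration. Present the unadjusted and adjusted group differences, each with a 95% confidence interval, side by side.
3. Where the adjusted result no longer supports a difference, describe the metabolite as not separable from disease duration, not as a marker of probable sarcopenia.
4. State as a limitation that no fibromyalgia severity score is listed as recorded, so confounding by severity would remain, and describe the result as an association with low grip in fibromyalgia.

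The cost is a few lines of analysis plan, one extra model per metabolite and one residual degree of freedom. There may be a small loss of precision, most likely where groups are imbalanced on duration and the metabolite is only weakly related to it. No new measurement is needed.

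### Does grouping patients on grip strength alone, with muscle mass unused in the metabolite analyses, undermine a study titled as one of sarcopenia?

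*Combined protocol and SAP*

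**What the plan says.** The official title is "Determination of Metabolomic Profile Differences in Sarcopenia Accompanying Fibromyalgia Syndrome". The opening section of the combined protocol and SAP describes two measurements, taken in patients and controls alike: "Patients with fibromyalgia and healthy volunteers were screened for sarcopenia by using hand grip strength measurement with a hand dynamometer, muscle mass measurement" by bioimpedance. It then gives one classification rule, attributed to EWGSOP2: "patients with hand grip strength below 16 kg were considered to have probable sarcopenia". On that rule 22 patients are in the group with probable sarcopenia (FMS PS+) and 22 in the group without it (FMS PS-). The 22 controls are described as free of sarcopenia, and the only result given for them is a grip above 16 kg.

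The section on measurement of plasma metabolomics states that "Two-tailed t-test was performed between experimental groups and significantly changed metabolites were identified". The Statistical Analysis section adds: "After comparing the metabolome data between the three groups, cluster analysis was performed and pathway differences between the groups were revealed". Neither mentions muscle mass. For descriptive reporting, the Statistical Analysis section says "The numerical data obtained are given as mean and standard deviation, and categorical data are given as number (n) and percentage".

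**The concern.** The document separates two terms. Its rule and group names say probable sarcopenia; its title and its stated reason for screening say sarcopenia. It measures a second component, muscle mass, and then gives no index, no cut-off and no role for it in the metabolite analyses.

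The low-mass status of the 22 PS+ patients is therefore not stated. A reader who sees a metabolite difference between PS+ and PS- cannot tell whether it belongs to patients with weak grip only or to patients with weak grip and low muscle mass. If the result were presented under the title's unqualified term, it could be taken to say more than the groups support. The natural responses would be to report how many PS+ patients had low mass, to add an analysis adjusted for muscle mass, and to reword the title.

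**Working it through.** The plan states no effect size, SD, power or sample-size calculation, so there is no figure of its own to reproduce. The check sets the statements side by side and then asks what a further analysis would yield.

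**1. Group counts.** 22 PS+ and 22 PS- make 44 patients, as stated; with 22 controls the total is 66.

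**2. Label against rule.**

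| Place | Term used | Basis |
|---|---|---|
| Official title | Sarcopenia | none given |
| Classification rule | Probable sarcopenia | grip below 16 kg |
| Group names | With / without probable sarcopenia | same rule |
| Metabolite analyses | By group | same rule |

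Rule, group names and analyses agree with each other. Only the title differs, by one qualifier. The document contains no objective, hypothesis or conclusion that claims confirmed sarcopenia, and it does not define that condition.

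**3. Precision of the contrast as planned.** With 22 per group, a metabolite scaled to SD 1 and 42 degrees of freedom, the standard error is √(2/22) = 0.302. The 95% half-width is 2.018 × 0.302 = 0.61 SD. Power of 80% at two-sided 0.05 requires a difference of 0.86 SD.

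**4. What adjustment for muscle mass would give.** Let ρ be the correlation between group and muscle mass. The standard error becomes √(2/22)/√(1 − ρ²), with 41 degrees of freedom and a t quantile of 2.02. The values of ρ and the effect sizes are assumptions. Power is from the noncentral t distribution, per metabolite, with no multiplicity allowance.

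| ρ | 95% half-width (SD) | Power at 0.45 SD | Power at 0.9 SD | Effect for 80% power (SD) |
|---|---|---|---|---|
| 0.3 | 0.64 | 28% | 79% | 0.91 |
| 0.5 | 0.70 | 24% | 71% | 1.00 |
| 0.7 | 0.85 | 18% | 55% | 1.21 |

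For example, at ρ = 0.5: 0.302/√0.75 = 0.348, and 2.02 × 0.348 = 0.70.

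The table keeps the residual SD at 1 before and after adjustment, which means muscle mass has no association with the metabolite within groups. If it had one, the residual SD would fall and the half-widths with it.

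**5. What the adjusted estimate would mean.** It is the group difference not explained by muscle mass. If it persists, it points to grip, which is what the groups are already named for. If it shrinks, intervals this wide would rarely show that muscle mass explains the difference. Neither outcome would justify the unqualified term in the title. Muscle mass is also part of the study's own sarcopenia screening, so adjusting for it may remove part of the condition under study.

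**6. What a mixed PS+ group would do.** Suppose a metabolite differs by 0.845 SD (80% power by the normal approximation) only in PS+ patients with low mass, and in no PS- patient, with the SD held at 1. If that share is 100%, 75%, 50% or 25%, the group difference is 0.845 × share = 0.84, 0.63, 0.42 or 0.21 SD, and power is 80%, 56%, 29% or 10%. The documents do not give the share. Dilution would make a mass-specific signal harder to find; it would not make the low-grip comparison wrong.

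**The case for a change.** The best case for acting is that the remedy is cheap and the gap is real. The study took the measurement, so stating the index and cut-off and giving one count would tell the reader who the PS+ patients are. The Statistical Analysis section promises a mean and SD for numerical data, but those cannot give a low-mass count without a cut-off. The phrase about appropriate parametric or non-parametric tests concerns distributional form and commits to no use of muscle mass. On this view even a weak adjusted analysis is harmless if it is labelled exploratory and shown beside the unadjusted contrast.

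Part of this stands. The index and cut-off are unstated, and a count in PS+ would help a reader. But that is detail which authors normally supply when they describe their groups. The descriptive sentence covers most of it: mean and SD for muscle mass, and number and percentage once a category is defined. Nor is there much reason to doubt that the values exist, because grip strength appears in the same screening sentence and was evidently kept.

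The argument for the adjusted model is weaker. In an untargeted screen it would add a second set of imprecise estimates to a question the study was not set up to answer.

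**Conclusion.** The observations are correct, but no change to the plan follows. All 44 patients are grouped on grip alone, no described metabolite analysis uses muscle mass, and the title leaves out a qualifier that the rule and both group names carry. The PS+ versus PS- comparison remains a valid contrast of low with adequate grip, and no sample-size, alpha or power figure is affected.

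The three possible remedies add little. The unstated index and cut-off are a gap that analysts fill sensibly in the description of the groups. The title is a matter of wording, best read with the group names. The adjusted analysis is a debatable trade-off: a half-width of 0.64 to 0.85 SD against 0.61 SD, and 18% to 28% power at 0.45 SD, for an estimate that could not settle the title. The document is dated January 2023 and describes recruitment from May to December 2022 in the past tense, so the grouping itself is fixed.

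This conclusion assumes that results are reported under the group names the plan uses. The adjusted figures rest on assumed correlations and effect sizes. The effect of muscle mass on any metabolite result cannot be derived from the documents.

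### The 66 GC/MS runs span at least 40.7 hours, injection order is not stated, and the group comparison has no run-position term, so metabolite-specific drift would bias it if order is associated with group.

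*Combined protocol and SAP*

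**What the plan says.** The opening description of the study gives the sample: "This study included 44 female patients aged 18-60", split into 22 FMS PS- and 22 FMS PS+, and "22 female healthy controls". The section on measurement of plasma metabolomics follows the statement that "Plasma samples were collected from all participants".

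That section gives the oven programme and the run length: "The analysis took a total of 37 minutes". On correction of signal intensity it says: "Normalization processes were also carried out according to the total ion chromatogram". On the group comparison it says: "Two-tailed t-test was performed between experimental groups and significantly changed metabolites were identified". FAME mix standards are named, but no use of them to correct intensities along the run sequence is described.

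The Statistical Analysis section adds a choice between parametric and non-parametric tests according to normality, a three-group comparison, cluster analysis and a 0.05 significance level.

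Neither section mentions injection order, randomisation or blocking of runs, batches, pooled quality-control samples, or a run-position term.

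**The concern.** All results come from one instrument over a sequence lasting the better part of two days. Quantification is semi-quantitative, from peak areas and heights, so any change in response over the sequence that is left after normalisation enters the result directly.

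Total ion chromatogram scaling applies one factor to every peak in a sample. It removes drift common to all peaks but not drift that differs between metabolites. The t-test has no term to absorb what remains, and a rank test would not help, because a shift in location affects it as well.

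If one group tended to be injected later than another, a metabolite with no true group difference could be listed as changed. Multiplicity control would not cure this, because the shift is systematic and largest for the metabolites that drift most. It would also carry into the cluster and pathway results.

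**Working it through.** **Run length.** The oven holds at 70°C for 1 minute, "then increased to 320°C in increments of 10 degrees per minute and remained for 10 minutes". The sum is 1 + (320 − 70)/10 + 10 = 1 + 25 + 10 = 36 minutes, against 37 stated. The 1-minute gap is immaterial. The text adds "Afterwards, the system returned to its original temperature" without a duration, so cool-down may or may not lie inside the 37 minutes.

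**Instrument time.** Samples: 44 + 22 = 66, assuming one injection per participant (replicates are not mentioned). 66 × 37 = 2,442 minutes = 40.7 hours. With the 36-minute sum it is 66 × 36/60 = 39.6 hours. The 40.7 hours is a minimum if blanks, standards or cool-down are extra. For example, an assumed 5 to 15 minutes more per run gives 66 × 42/60 = 46.2 to 66 × 52/60 = 57.2 hours.

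**Effect on the t-test if groups were run one after another.** The documents give neither drift nor between-person variability, so the following are assumptions: group-by-group order, linear metabolite-specific drift left after scaling, 22 per group, no true difference, two-sided test at 0.05.

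- Mean positions of adjacent groups are 22 places apart, and of first and last 44 places apart, out of 65 steps. The shares of total drift are 22/65 = 0.34 and 44/65 = 0.68, taken below as f = 1/3 and 2/3.
- Noncentrality = (drift × f / CV) × √(22/2), with 42 degrees of freedom and critical value 2.018.
- Example: drift 20%, CV 30%, first versus last. (0.20 × 2/3 / 0.30) × √11 = 0.444 × 3.317 = 1.474, which gives a rejection rate of 30.2%.

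False-positive rate, adjacent / first versus last (nominal 5%):

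| Assumed drift | CV 30% | CV 50% | CV 80% |
|---|---|---|---|
| 10% | 6.5% / 11.1% | 5.5% / 7.2% | 5.2% / 5.8% |
| 20% | 11.1% / 30.2% | 7.2% / 13.9% | 5.8% / 8.4% |
| 30% | 19.1% / 57.9% | 9.9% / 25.4% | 6.9% / 12.8% |

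**Effect of order.** A simulation (20,000 replicates) used total linear drift of 0.25, 0.5 and 1.0 within-group SD. Rejection rates for the same pair of groups (first-run versus last-run under consecutive blocks):

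| Order | 0.25 SD | 0.5 SD | 1.0 SD |
|---|---|---|---|
| Consecutive group blocks | 8.5% | 19.7% | 58.6% |
| Fully random | 4.9% | 4.9% | 4.7% |
| Balanced blocks of three | 4.7% | 4.8% | 4.2% |

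The inflation therefore comes from the association between order and group, not from drift alone.

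**Can group and position be separated under consecutive blocks?** Position varies within each block, so a model with three groups and one common linear slope is estimable. The within-group sum of squares of position is 3 × 22 × (22² − 1)/12 = 2,656.5. In units of the residual variance:

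- Unadjusted variance of a group difference: 2/22 = 0.0909.
- Adjusted, adjacent groups: 0.0909 + 22²/2,656.5 = 0.0909 + 0.1822 = 0.2731. The ratio is 3.00 and the standard error is 1.73 times as large.
- Adjusted, first versus last: 0.0909 + 44²/2,656.5 = 0.0909 + 0.7288 = 0.8197. The ratio is 9.02 and the standard error is 3.00 times as large.

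**The case against.** The strongest objection is that the document is silent on order, and silence is not evidence of a bad order. A reader might infer that the injections were unbalanced or run group by group. Nothing in the text says so. The laboratory may have randomised the runs without reporting it, and in that case the t-test keeps its error rate near 5%. This part stands, and the bias is therefore stated only as conditional.

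The size also depends on assumptions that the document cannot confirm. Drift of 20% with a CV of 30% gives a striking first-versus-last rate, but at a CV of 80% the same drift barely moves it. This stands too, so a range is shown.

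A reader might go further and infer that, under consecutive blocks, run position and group are one and the same variable and no adjustment is possible. Under linear drift that is wrong: the adjusted contrast can be estimated, with a large loss of precision and reliance on linearity and a common slope.

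Finally, the text is in the past tense, so a prospective run list is probably no longer available. That limits the remedy but leaves the analysis change open. What the objection does not remove is that the analysis as described has no step that deals with metabolite-specific drift, and that a reader cannot tell from the document whether one was needed.

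**Conclusion.** The concern holds in conditional form. The runs need at least 40.7 hours of instrument time (one injection each assumed), neither order nor balance is stated, and the described normalisation and test leave metabolite-specific drift in the group comparison. Whether this biased any result depends on the actual order, which the document does not give, so bias is possible but not shown.

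Under the assumed worst-case order with 20% residual drift, the false-positive rate for a null metabolite runs from 6%/8% (CV 80%) to 11%/30% (CV 30%), adjacent / first versus last. This is a change that should be made, because the check is cheap and bears on every metabolite comparison.

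**What to change.** 1. Take injection order from the GC/MS file time stamps and tabulate it by group (FMS PS+, FMS PS-, control).
2. Replace the plain t-test with a linear model for each metabolite containing group and run position.
3. If any samples are still to be run, inject them in blocks of one FMS PS+, one FMS PS- and one control, with random order within each block.
4. If the groups were run as consecutive blocks, state that the adjusted comparison relies on linear drift with a common slope and that its standard error is about 1.7 times (adjacent groups) to 3 times (first versus last) that of the unadjusted one. Do not present metabolites that lose significance after adjustment as established group differences.

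**Cost.** No new samples are needed. If order was near balanced, the cost is one degree of freedom and a short table. If it was not, the cost is a substantial loss of precision and weaker conclusions.

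### Scaling to the total ion chromatogram can shift unchanged metabolites if a dominant peak differs between groups, and the plan describes no check that would show it

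*Combined protocol and SAP*

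**What the plan says.** The section 'Measurement of plasma metabolomics' describes an untargeted GC/MS assay ("Untargeted metabolomics studies have been conducted") with relative quantities only: "Peak areas and heights were used in semi-quantitative analysis". On scaling it says: "Normalization processes were also carried out according to the total ion chromatogram". The next sentence is the group comparison: "Two-tailed t-test was performed between experimental groups and significantly changed metabolites were identified". Pathway analysis follows.

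The same section says "In this study, FAME mix standards were used as standards in the system", but gives that mixture no role in scaling intensities. The 'Statistical Analysis' section adds a normality check, a choice between parametric and non-parametric tests, cluster analysis and a 0.05 significance level. Neither section mentions an internal-standard, pooled-QC or median-based normalisation, a log-ratio analysis, a comparison of total signal between groups, or a sensitivity analysis on normalisation. There are 22 women in each of the three groups.

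**The concern.** Total-ion scaling treats the total signal as a neutral measure of how much material was injected. It is neutral only if total signal does not differ between groups for biological reasons. If a peak that makes up much of the total is truly higher in one group, the divisor is larger there, and every unchanged metabolite appears lower in that group. If the peak is lower, the others appear to rise.

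The displacement is common to all the other metabolites, so the resulting false signals mostly point one way and can look like a coherent biological pattern. They would then feed the clustering and pathway steps, which are the study's main outputs. The same displacement can hide a real change that runs in the direction of the dominant peak. Choosing a non-parametric test instead of a t-test does not help, because the scaled values themselves are displaced.

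**Working it through.** The documents contain no power or error-rate figure to reproduce, so the check starts from the mechanism.

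**Inputs from the documents:** total-ion scaling; two-tailed test per metabolite; alpha 0.05; 22 per group.

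**Assumed, because the documents do not give them:** share *s* of total signal held by the dominant peak; proportional rise *r* of that peak in one group; between-person log-SD of 0.3 to 0.5; about 100 metabolites; tests on log values.

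**Step 1: shift.** With the total set to 1 in the reference group, it becomes 1 + *s r* in the other. Each unchanged metabolite is therefore multiplied by 1/(1 + *s r*):
- *s* = 0.10, *r* = 0.25: 1/1.025 − 1 = −2.4%
- *s* = 0.20, *r* = 0.50: 1/1.10 − 1 = −9.1%
- *s* = 0.30, *r* = 0.50: 1/1.15 − 1 = −13.0%

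**Step 2: false-positive rate, normal approximation.** The standard error of a log difference is SD × √(2/22), which is 0.0905 at SD 0.3 and 0.151 at SD 0.5. With z = ln(1 + *s r*)/SE, the rejection probability is Φ(z − 1.96) + Φ(−z − 1.96).

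**Step 3: simulation.** 400 replicates per setting, 22 against 22, about 100 metabolites with one dominant peak. Probabilistic quotient (median-ratio) scaling was run on the same data.

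| Share, rise | Log-SD | z | Approximation | Simulated, total-ion | Simulated, quotient |
|---|---|---|---|---|---|
| 10%, +25% | 0.3 | 0.27 | 5.9% | 5–6% | about 5% |
| 10%, +25% | 0.5 | 0.16 | 5.3% | 5–6% | about 5% |
| 20%, +50% | 0.3 | 1.05 | 18.4% | about 17% | about 5% |
| 20%, +50% | 0.5 | 0.63 | 9.7% | about 9% | about 5% |
| 30%, +50% | 0.3 | 1.54 | 33.9% | 28–30% | about 5% |
| 30%, +50% | 0.5 | 0.93 | 15.3% | 13–14% | about 5% |

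With no group difference in the dominant peak, total-ion scaling also gives about 5%. At a 20% share and +50%, over 90% of the false positives point the same way.

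**Step 4: effect of multiplicity correction.** Mean number of false positives among 99 unchanged metabolites, before and after Benjamini-Hochberg at 5%:
- 20%, +50%: about 17 falls to 1.4–1.9 (SD 0.3); about 9 falls to 0.2–0.3 (SD 0.5)
- 30%, +50%: 28–30 falls to 7.4–8.4 (SD 0.3); 13–14 falls to 0.7–1.1 (SD 0.5)

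Control is not fully restored. At a 20% share and +50%, at least one false positive survived in 17–45% of replicates, where about 5% is expected.

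**Step 5: masking.** Take a true 30% rise in the same group, with SD 0.3, a 30% share and +50%. Under unbiased scaling, z = ln 1.30/0.0905 = 2.90 and power is Φ(2.90 − 1.96), about 83%. Under total-ion scaling, z = (ln 1.30 − ln 1.15)/0.0905 = 1.35 and power is about 27%.

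**The case against.** Total-ion scaling is a recognised choice in semi-quantitative, untargeted work, and leaving out a second normalisation contradicts nothing in the plan. Harm needs two things together: a peak holding roughly 20–30% or more of the signal, and a true difference of roughly 25–50% in that same peak. Nothing in the documents shows either, and the exclusion of endocrine disease, organ failure, systemic glucocorticoids and sulfonylureas removes some causes of large metabolic differences. All of this stands, and it is why the point is conditional.

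Three stronger readings are tempting, and none is supported:
- *The results are biased.* A reader might infer this from the arithmetic, but the size depends wholly on quantities that the documents do not report.
- *False-discovery-rate control would not help.* It is true that the null hypothesis is false on the scaled data, but step 4 shows that the correction removes most of the excess. Much of the raw count comes from using an uncorrected 0.05 threshold, which is a separate matter.
- *No check was made.* That total-ion scaling stood alone is inferred from silence in a short methods description. It shows that no check is documented, not that none was done.

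Quotient scaling is not a gold standard either. It assumes that most metabolites do not change, and it is no better than total-ion scaling when many truly move together.

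What the objection does not answer is that nothing described in the plan would tell a reader whether the key assumption held.

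**Conclusion.** The point holds as a conditional risk with a cheap remedy. The direction of the effect is arithmetic; its size is assumed. At 22 per group and log-SD 0.3–0.5, it is negligible for a 10% share with a 25% rise (5–6% against a nominal 5%). It is material for a 20% share with a 50% rise (shift about −9%, false-positive rate about 9–17%) and larger at a 30% share (about −13%, 13–30%). It vanishes if the dominant peak does not differ between groups. This is a desirable improvement and does not invalidate the analysis. Without it, a list of changed metabolites that mostly move one way cannot be told apart from a scaling artefact.

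**What to change.** Keep total-ion scaling as the main analysis and add the following:
1. Report the unscaled total ion signal, and the share held by the largest peaks, for each of the three groups, with estimates and intervals. Do not rely on a significance test alone: with 22 per group it could miss a modest difference.
2. Repeat all contrasts as a sensitivity analysis, either after probabilistic quotient (median-ratio) normalisation or with the dominant peaks left out of the total.
3. Show both sets of results and flag metabolites whose direction or significance depends on the normalisation.
4. Repeat the pathway analysis under the second normalisation, and do not present normalisation-dependent metabolites or pathways as firm findings.

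Do not require significance under both methods. Such a rule inherits the masking in step 5, where power could not exceed about 27% for an effect that unbiased scaling detects about 83% of the time.

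The cost is one re-analysis of existing data, with no new samples or assays, and possibly weaker conclusions for some metabolites. Because quotient scaling has its own assumption, it serves as a check and not as a replacement.
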